## **Primary Aim of this study**

To evaluate the effectiveness of a two-month interactive school-based oral health education program in reducing periodontal disease among 15-year-old students in Nablus City, Palestine, using clinical indices such as the Community Periodontal Index for Treatment Needs (CPITN) and the Simplified Oral Hygiene Index (S-OHI).

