### **Clinical Screening**

In this study, the Community Periodontal Index for Treatment Needs (CPITN) was used to assess the prevalence of periodontal disease (PD) among 9th-grade students before and after the intervention. For adolescents, CPITN scores 0, 1, and 2 are used to assess gingivitis:

- Score 0: Healthy gingiva
- Score 1: Gingival bleeding observed after gentle probing
- Score 2: Presence of supra or sub-gingival calculus

For adults, CPITN includes the following scores for periodontitis:

- Score 3: Pathological pockets measuring 4 to 5.99 mm deep

Score 4: Pathological pockets measuring 6 mm or deeper

Each sextant of the mouth examined was assigned a code number, with the index teeth representing each sextant: 16, 11, 26, 36, 31, and 46 (22).

The Oral Hygiene Index-Simplified (OHI-S) was used to determine the oral hygiene status of the subjects. This index consists of two components: debris and calculus, each with a possible score range of 0 to 3. The amounts of calculus and debris were assessed by examining the facial surfaces of teeth numbers 11, 16, 26, and 31 and the lingual surfaces of teeth 36 and 46. The scores for calculus and debris were added together and divided by the number of examined surfaces to calculate the OHI-S score for each individual.

In the pilot phase of the study, the Interclass Correlation Coefficient (ICC) was calculated to assess the reliability of the clinical measurements. A total of 20 students were examined five times by five data collectors, resulting in ICC values of 0.83 for CPITN and 0.98 for OHI-S, indicating high reliability.

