Statistical Analysis Plan (SAP)

Official Title: Effectiveness of an Interactive School-Based Oral Health Education Program in Reducing Periodontal Disease Among Palestinian Adolescents: A Double-Blind Intervention Study

NCT Number:

Document Date: March 1, 2024

Sponsor: Al-Quds University

Overview

This Statistical Analysis Plan outlines the statistical methods and procedures used to analyse data for the intervention study assessing the effect of a school-based oral health education program on periodontal conditions and related behaviours among 9th-grade students in Nablus City, Palestine.

Study Objectives

- Primary: To evaluate the effectiveness of the intervention on CPITN and S-OHI scores.
- Secondary: To assess changes in oral hygiene practices, dietary habits, and smoking behaviours.

Data Preparation and Management

Data were entered into IBM SPSS Statistics version 25.0.

All data were reviewed for completeness and consistency prior to analysis.

Normality testing was conducted using Shapiro-Wilk tests.

Missing data was minimal and handled by complete case analysis.

Statistical Analyses

Descriptive statistics will be used to summarise baseline characteristics by group (mean \pm SD, frequencies, percentages).

- Paired t-tests will be used to assess within-group differences from baseline to post-intervention.
- Independent t-tests were used to compare mean differences between the intervention and control groups.
- Statistical significance was set at $p < 0.05$.
- Confidence intervals were calculated at the 95% level for all primary outcomes.

Study Questions VS Analysis Plan

1. Can interactive educational sessions reduce **Community Periodontal Diseases Index** scores among 9th-grade students in Nablus City for two months?

1. Data Type and Variables

Dependent Variable: Community Periodontal Index for Treatment Needs (CPITN) **score** → Continuous quantitative variable

Independent Variable: Group type (Intervention vs. Control) → Binary categorical variable

Time Points: Pre-intervention (baseline)

Post-intervention (after two months) → true experimental design (pre-post measurements)

2. Statistical Design

Since there are two time points and two groups, the analysis includes:

A. Within-Group Analysis (Intervention group and control group):

Purpose: To assess whether there is a significant reduction in CPITN scores after the interactive educational sessions within the two groups themselves.

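### CPITN and S-OHI are unranked primary outcomes for an aim of reducing periodontal disease, with no success rule, so an S-OHI result alone could be presented as meeting that aim

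*SAP*

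**What the plan says.** The protocol's Primary Aim concerns an "interactive school-based oral health education program in reducing periodontal disease among 15-year-old students", and it names CPITN and S-OHI together, unranked, as the measures for that aim. The SAP's title also speaks of reducing periodontal disease. Its Study Objectives read "Primary: To evaluate the effectiveness of the intervention on CPITN and S-OHI scores", without ranking the two, and its Statistical Analyses list refers to primary outcomes in the plural.

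The protocol's Clinical Screening section separates the indices. CPITN "was used to assess the prevalence of periodontal disease (PD) among 9th-grade students before and after the intervention". By contrast, "The Oral Hygiene Index-Simplified (OHI-S) was used to determine the oral hygiene status of the subjects". OHI-S is built from a debris score and a calculus score. The same section adds: "For adolescents, CPITN scores 0, 1, and 2 are used to assess gingivitis". Scores 3 and 4, for pathological pockets, are listed for adults.

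In the SAP, CPITN is Study question 1 and S-OHI is Study question 2. Each has its own independent t-test, under one general threshold of p < 0.05. Neither document gives a testing order, a division of alpha, or a rule on whether one or both indices must be significant before the programme is called effective.

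**The concern.** The claim is about disease, but by the protocol's own definitions only one of the two primary indices assesses disease. With no success rule, the authors can decide after seeing the results which index carries the conclusion. Two things are at stake.

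- **Interpretation.** A real improvement in oral hygiene, with no demonstrated change in CPITN, could be reported under a title and aim about periodontal disease. Adjusting alpha would not prevent this, because the S-OHI effect would be genuine but would not be a disease effect.
- **Error rate.** If a result on either index is accepted, the primary claim has two chances to succeed by luck, each at 0.05.

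A related wording issue is that, in this age group, CPITN covers bleeding and calculus only. Even a CPITN success is therefore narrower than the phrase periodontal disease suggests.

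**Working it through.** The plan gives no overall false-positive rate to reproduce. Its only figure on this point is the per-test threshold of 0.05 (SAP, Statistical Analyses).

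**Inputs**
- Alpha is 0.05 for each index. Sidedness is not stated; two-sided is assumed, so the critical value is 1.96.
- There are two primary between-arm tests (Study questions 1 and 2).
- The correlation r between the two test statistics is not in the documents. Values of 0, 0.5 and 0.8 are assumed. Both indices score calculus (CPITN score 2 and the OHI-S calculus component), so a positive value is likely.
- The planned numbers are 536 intervention and 410 control students (protocol, sample size paragraph).

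**Step 1. Either index suffices, no true effect on either.** With (Z1, Z2) standard bivariate normal:

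P(at least one significant) = 1 − P(|Z1| < 1.96 and |Z2| < 1.96)

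P(at least one significant in favour of the programme) = 1 − P(Z1 < 1.96 and Z2 < 1.96), with Z signed so that positive favours the programme.

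| r | Either direction | Favourable only |
|---|---|---|
| 0 | 1 − 0.95² = 0.0975 | 1 − 0.975² = 0.0494 |
| 0.5 | 1 − 0.9093 = 0.0907 | 1 − 0.9546 = 0.0454 |
| 0.8 | 1 − 0.9219 = 0.0781 | 1 − 0.9610 = 0.0390 |
| One index only | 0.05 | 0.025 |

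**Step 2. Both indices required.** A false joint claim needs a false positive on at least one index that has no true effect, so its rate cannot exceed 0.05. If neither index is affected and r = 0, it is 0.05² = 0.0025.

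**Step 3. Hygiene-only illustration.** Suppose S-OHI truly improves by d standard deviations and CPITN does not change. The effect sizes are assumed, the test statistics are taken as independent, and clustering is ignored.

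SE = √(1/536 + 1/410) = 0.0656

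- d = 0.2: mean of Z = 0.2/0.0656 = 3.05, so power for S-OHI = 0.862. Multiplying by 0.95 (CPITN not significant) gives 0.82.
- d = 0.3: mean of Z = 4.57, so power = 0.996. Multiplying by 0.95 gives 0.95.

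If only a favourable CPITN result counts as significant, the factor is 0.975 and the results are 0.84 and 0.97. In this scenario, S-OHI significant without CPITN would be the usual outcome, and the plan does not say how to report it. Clustering by school would lower these probabilities.

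**The case against.** **S-OHI alone as sufficient.** A reader might infer that, as written, a significant S-OHI result with no change in CPITN meets the primary objective. The documents do not support that. The objective joins the indices with *and*, which allows a both-required reading at least as easily as an either-suffices one. The two separate study questions allow a third reading, in which each index is answered on its own. What stands is that the rule is undefined and nothing excludes the permissive reading.

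**9.75% as the trial's error rate.** This figure holds only if either index suffices and r = 0. It also counts significant results against the programme, which could not support a claim of benefit. The favourable-only figures (4.9% to 3.9%, against 2.5%) are the fairer measure of a false claim of benefit. The inflation remains, but it depends on the reading.

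**S-OHI as plaque only, and as the likelier success.** OHI-S includes calculus, which is also a CPITN score, so the split between hygiene and disease is not clean. The documents give no expected effect for either index. Sessions 2 and 4 teach brushing and flossing, so hygiene is a direct target, but no ranking of likely success follows.

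**The CPITN limits are disclosed.** Clinical Screening does say that scores 0 to 2 assess gingivitis in adolescents. That helps a careful reader, but the title and aim still use the broader term.

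**Timing.** Much of the text is in the past tense. If results are known, ranking the outcomes now is a post hoc change. That is a reason to disclose it, not to leave the rule undefined.

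**Conclusion.** The concern holds as a missing success rule combined with a mismatch between aim and index. The sponsor should correct it. Two primary outcomes are not wrong in themselves. The fault is that they are unranked, one is defined as oral hygiene status, and the aim and title claim a reduction in disease.

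The interpretive problem matters more and does not depend on any assumed correlation. The error-rate problem is conditional: 9.75% to 7.8% overall, or 4.9% to 3.9% in the favourable direction against 2.5% for one index, if either index suffices; at most 5% if both are required. These figures assume two-sided tests, approximately normal test statistics and correlations of 0 to 0.8.

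A reader might also infer that relying on CPITN alone guarantees a 5% error rate. It does not. That level is nominal and assumes that any clustering by school is handled separately. The protocol refers to intervention and control schools, while the SAP uses student-level t-tests.

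**What to change.** In SAP Study Objectives, and in the protocol's Primary Aim to match:

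1. State that the periodontal-disease conclusion rests on the between-arm CPITN comparison (Study question 1).
2. Name one test for it. The Statistical Analyses list compares mean differences between the groups, whereas Study question 1 compares post-intervention scores.
3. Test S-OHI (Study question 2) second in a fixed sequence, with a confirmatory claim only if CPITN succeeds. Interpret it as oral hygiene status only.
4. Word a CPITN success as a reduction in gingival bleeding and calculus (scores 0 to 2).
5. If outcome data have already been seen, date the change and disclose it as post hoc.

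**Cost.** The change is to wording and needs no new data or extra students. The price is that an S-OHI result on its own can no longer be claimed as a primary success, and Study question 2 loses its confirmatory answer if CPITN fails. Requiring both indices, or splitting alpha at 0.025 each (overall 1 − 0.975² = 0.0494 if independent), would also control the error rate. An alpha split would still need the explicit statement that S-OHI is read as oral hygiene.

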### **Instrument Development**

The questionnaire utilised in this study was adapted from existing literature with modifications to align with the study's primary objective. The secondary aim was to evaluate the impact of the interactive oral education program on students' oral hygiene practices, dietary habits, and smoking behaviours two months after the implementation of the educational sessions. Initially, the questionnaire was developed in English and later translated into Arabic. To ensure accuracy, the translation was validated through a back-translation process from Arabic to English before being administered as a pre-test.

The questionnaire consisted of pretested standardised closed-ended questions that were assessed for face and content validity by three experts in the field. It was divided into five sections:

1. **Student Background:** This section included questions about the type of school (governmental or private) and the school system.
2. **Family Background:** The questions covered family size, parents' educational and occupational status, and the family's economic status.
3. **Oral Hygiene Practices:** This section addresses the frequency and technique of tooth brushing.
4. **Dietary Habits:** Questions focused on the frequency of breakfast consumption per week and the daily intake of nutritious versus non-nutritious foods.
5. **Smoking Behaviours:** This section assessed the frequency of cigarette and water pipe smoking and the number of cigarettes consumed.

The questionnaire's internal consistency was also evaluated using Cronbach's alpha, yielding a reliability coefficient of 0.967 for the 47 items tested.

The questionnaire was administered through direct interviews with individual students. All participants completed the questionnaire and underwent clinical examinations, resulting in

a 100% response rate. The questions in the questionnaire were designed to align with the topics covered in the educational program.

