Test to use: Paired t-test, as the data is normally distributed.

B. Between-Group Analysis (Post-intervention comparison):

Purpose: To compare the post-intervention CPITN scores between the intervention and control groups.

Test to use: Independent T-test as the data is normally distributed

Note: The two groups were examined for their differences in baseline measurement.

2. Can interactive educational sessions reduce **S-Oral hygiene index scores** among 9th-grade students in Nablus City within two months?

1. Data Type and Variables

Dependent Variable: Simplified Oral Hygiene Index (S-OHI) score → Continuous quantitative variable

Independent Variable: Group type (Intervention vs. Control) → Binary categorical variable

Time Points: Pre-intervention (baseline)

Post-intervention (after two months) → true experimental design

2. Statistical Design

Since there are two time points and two groups, the analysis includes:

A. Within-Group Analysis (Intervention group only):

Purpose: To assess whether there is a significant improvement (reduction) in S-OHI scores after the interactive educational sessions.

Test to use: *Paired t-test*, as the data is normally distributed.

B. Between-Group Analysis (Post-intervention comparison):

Purpose: To compare the post-intervention S-OHI scores between the intervention and control groups.

Test to use: *Independent t-test*, as the data is normally distributed

3. Will oral hygiene practices, smoking habits, and dietary habits improve among 9th-grade students after interactive educational sessions are applied in Nablus City?

Questionnaire responses related to oral hygiene practices, dietary habits, and smoking behaviour were **recoded** into scale variables to facilitate the computation of mean scores pre-and post-intervention. Correct answers reflecting preventive behaviours, in line with American Dental Association (2023) guidelines, were assigned the highest scores, while incorrect responses received the lowest scores, for example:

- "Do you clean your teeth?": Yes = 1, No = 0
- "How often do you clean your teeth?": Once/day = 1, Twice/day = 2, Three times/day = 3
- "How long does it take to clean your teeth?": One minute = 1, Two minutes = 2, More than two minutes = 3, Don't know = 0
- "Brushing technique": Scrubbing = 1, Bass = 2, Modified Bass = 3
- "Toothbrush type": Hard bristle = 1, Soft bristle = 2, Medium bristle = 3

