Appendix A

Section 2: Oral Hygiene Practices

The question	Responses	Old codes	New scores
B.1 – Do you brush your teeth?	Yes	1	1
	No.	2	0
B1.1 How often do you usually brush your teeth?	Once a day	1	1
	Twice a day or more	2	2
	Sometimes	3	3
B.1.3 - How long do you spend brushing your teeth?	A minute or less	1	1
	Two minutes	2	2
	More than two minutes	3	3
B.1.4 - How do you brush your teeth?	Bass method	1	2
	Scrubbing method	2	1
	Modified Bass method	3	3
	Other	4	0
B.1.5 - What kind of bristles does your toothbrush have?	Soft bristles	1	2
	Medium bristles	2	3
	Hard bristles	3	1
	I am not sure	4	0
B.1.6 - How often do you change your toothbrush?	Every month	1	3
	Every two months	2	2
	Every three months	3	1
	Other	4	0
B.1.7 - Do you use other oral and dental cleaning tools besides the toothbrush?	Dental floss	1	3
	Interdental brush	2	2
	Mouthwash	3	1
	Do not use	4	0
B.1.8 - Do you visit the dentist in your life?	Yes.	1	1
	No.	2	0
B.1.9- How did you visit the dentist?	Regularly	1	3
	Sometime	2	2
	Pain	3	1
	Before 6 months	1	3
	Before 6-12 months	2	2

B.1.10 - When was the last time you visited the dentist?	Before 1-2 years	3	1
	Before 3-5 years	4	0
B.1.11 - If you visited the dentist, what was the purpose of your visit?	Pain	1	0
	Recommendation from a friend or relative	2	1
	Recommendation from another dentist	3	2
	Routine dental check-up	4	3
	Teeth and gum cleaning	5	4

Section 3: Diet Habits

C.1.1 - Do you eat breakfast on weekdays?	Never	1	0
	Once a week	2	1
	Twice a week	3	2
	Three times a week	4	3
	Four times a week	5	4
	Every day	6	5
C.2.1-Do you have breakfast on weekends?	Never	1	0
	Once a week	2	1
	Every weekend	3	2

C.2 - How often do you eat or drink the following items? (Tick one box for each item by marking an "X" under the option that applies to you in each row):

Item	Never	Less than once a week	Once a week	2-4 times a week	6 times a week	Once a day	More than once a day
Fruits	0	1	2	3	4	5	6
New code	0	1	2	3	4	5	6
Vegetables	0	1	2	3	4	5	6
New code	0	1	2	3	4	5	6
Sweets (e.g., candy or chocolate)	0	1	2	3	4	5	6
New code	6	5	4	3	2	1	0
Soft drinks or any sugar-containing beverages	0	1	2	3	4	5	6
New code	6	5	4	3	2	1	0
Milk and dairy products	0	1	2	3	4	5	6

New code	0	1	2	3	4	5	6
Red meat	0	1	2	3	4	5	6
New code	0	1	2	3	4	5	6
Fish	0	1	2	3	4	5	6
New code	0	1	2	3	4	5	6
Water	0	1	2	3	4	5	6
New code	0	1	2	3	4	5	6
Nuts	0	1	2	3	4	5	6
New code	0	1	2	3	4	5	6
Pastries	0	1	2	3	4	5	6
New code	6	5	4	3	2	1	0

Section 4: Smoking behaviours

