The question	Responses	Old codes	New scores
D.1- Do you currently smoke (at least one cigarette)?	Yes	1	2
	No	2	0
D.2 - How frequently do you smoke cigarettes or use other tobacco products?	Every day	1	1
	At least once a week but not every day	2	2
	Less than once a week	3	3
	I don't smoke	4	4
D.2.2 - If you smoke cigarettes, how many cigarettes do you usually smoke per week?	26 and over		0
	21-25 cigarettes		1
	16-20cigarettes		2
	11-15cigarettes		3
	6-10cigarettes		4
	0-5cigarettes		5
D.3 - Have you ever smoked a waterpipe (hookah)?	Yes	1	2
	No	2	0
D.4 - How often do you currently smoke a water pipe?	Every day	1	1
	At least once a week but not every day	2	2
	Less than once a week	3	3
	I don't smoke waterpipe	4	4

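### Appendix A has no score for non-brushers or never-attenders on five oral hygiene items, and puts D.2.2 only to smokers, so complete-case analysis can exclude students because of the behaviour being measured

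*SAP*

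**What the plan says.** The SAP's section on data preparation and management deals with missing values in one sentence: "Missing data was minimal and handled by complete case analysis". It does not say whether a case must be complete by item, by domain or by visit.

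Under the third study question, the answers on hygiene, diet and smoking "were recoded into scale variables to facilitate the computation of mean scores pre-and post-intervention". No formula follows: neither sum nor mean, and no minimum number of answered items. Each domain score then goes into a paired t-test in the intervention group and an independent t-test between groups.

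Appendix A lists the items and their new scores. One smoking item begins "D.2.2 - If you smoke cigarettes, how many cigarettes do you usually smoke per week" and one dental-visit item begins "B.1.11 - If you visited the dentist, what was the purpose of your visit". Neither has a code for a student to whom it does not apply.

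The Protocol, under Instrument Development, adds "The questionnaire was administered through direct interviews with individual students" and "All participants completed the questionnaire and underwent clinical examinations, resulting in" a response rate of 100%.

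**The concern.** A question that does not apply to a student differs from one left unanswered. The first is fixed by the student's behaviour, and here that behaviour is what the score measures. The SAP's only rule for an item without a value is complete-case analysis, and it does not separate the two situations.

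If a structural skip counts as missing, students leave the analysis because of their outcome. A non-brusher who starts brushing, or a student who sees a dentist for the first time, has no baseline hygiene score and so no place in the paired comparison. In the comparison at follow-up, the remaining non-brushers are absent from both groups. If the programme turns more non-brushers into brushers, it brings new and possibly low-scoring students into its own mean. In the smoking score, a student who stops could vanish at the visit that records the success.

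**Working it through.** **Which items lack a code (Appendix A, Sections 2 and 4)**

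| Score | Items | No code for | Items affected |
|---|---|---|---|
| Oral hygiene | 11 (B.1, B1.1, B.1.3 to B.1.11) | non-brusher | B1.1, B.1.3 |
| | | never-attender | B.1.9, B.1.10, B.1.11 |
| Smoking | 5 (D.1, D.2, D.2.2, D.3, D.4) | explicit non-smoker | D.2.2 |

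So 2 + 3 = 5 of 11 hygiene items and 1 of 5 smoking items are affected. B.1.4 to B.1.7 each have a residual answer worth 0. The SAP's main text gives brushing duration a don't-know answer worth 0, which Appendix A omits, but that does not describe a non-brusher either. The occasional-brushing answer in B1.1 scores 3, so it cannot stand in for never.

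**Oral hygiene score: one student**

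Take a student who brushes twice a day for two minutes by the Bass method, with a medium brush changed every two months and no other tools: 1 + 2 + 2 + 2 + 3 + 2 + 0 = 12 on the seven brushing items. The student has never seen a dentist (B.1.8 = 0).

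- Skips treated as missing: no score.
- Mean of the 8 answered items: 12/8 = 1.50.
- Skips scored 0: 12/11 = 1.09.

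An otherwise identical student who went once, in pain, one to two years ago adds 1 + 1 + 1 + 0 = 3 and scores 15/11 = 1.36. Averaging the answered items therefore ranks the never-attender higher (1.50 against 1.36).

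If the never-attender has a check-up during the study (B.1.8 = 1, B.1.9 = 2, B.1.10 = 3, B.1.11 = 3), the score becomes (12 + 9)/11 = 1.91. The gain is 0.82 with skips scored 0, 0.41 with the mean of answered items, and not observed with deletion.

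**Smoking score: a student who quits**

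A non-smoker without waterpipe use has D.1 = 0, D.2 = 4, D.3 = 0, D.4 = 4, a total of 8 over four items (mean 2.0). With D.2.2 = 5 the total is 13 (mean 2.6). In D.2.2 the code 0 belongs to the heaviest band, 26 cigarettes or more. Change on quitting, for smokers without waterpipe use:

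| Before quitting | Score (mean) | Blank deleted | Blank = 0 | Mean of answered items | D.2.2 = 5 |
|---|---|---|---|---|---|
| Less than weekly, 0 to 5 | 2+3+5+0+4 = 14 (2.8) | none | 8 − 14 = −6 | 2.0 − 2.8 = −0.8 | 13 − 14 = −1 |
| Weekly, 6 to 10 | 2+2+4+0+4 = 12 (2.4) | none | 8 − 12 = −4 | 2.0 − 2.4 = −0.4 | 13 − 12 = +1 |
| Daily, 26 or more | 2+1+0+0+4 = 7 (1.4) | none | 8 − 7 = +1 | 2.0 − 1.4 = +0.6 | 13 − 7 = +6 |

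**Group level, on assumptions**

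The documents give no prevalence or quit rate. Assume smoking prevalence p of 10% to 30%, quit rates of 30% (intervention) and 10% (control), and continuing smokers unchanged. The between-group difference in change is p × (0.30 − 0.10) × change on quitting. For the weekly smoker of 6 to 10 cigarettes:

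- D.2.2 = 5: 0.1 × 0.2 × 1 = +0.02 to 0.3 × 0.2 × 1 = +0.06.
- Blank = 0: 0.1 × 0.2 × (−4) = −0.08 to −0.24.
- Mean of answered items: 0.1 × 0.2 × (−0.4) = −0.008 to −0.024.
- Blank deleted: the effect of quitting is 0. Those kept are 536 × p × 0.7 = 38 to 113 and 410 × p × 0.9 = 37 to 111.

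For the heavy daily smoker the first three rules all give a positive difference (+0.12 to +0.36, +0.02 to +0.06 and +0.012 to +0.036). Hence the sign can turn on the unstated rule, but does not always do so.

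**The case against.** The strongest reply concerns smoking. D.1 and D.3 can be answered by everyone. D.2 has a non-smoker answer, and D.4 offers "I don't smoke waterpipe". The best band of D.2.2, "0-5cigarettes", includes zero, so an interviewer could place a non-smoker there. The data came from interviews that all participants completed, and missing data are called minimal. The questionnaire itself is not among the documents and may carry skip instructions.

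Most of this stands. A reader might infer that the smoking analysis is confined to current smokers, losing 70% to 95% of students at prevalences of 30% down to 5%, with a matching loss of power. The documents do not support that. It needs two unstated steps, a blank D.2.2 and listwise deletion, and it fits poorly with minimal missing data and full completion. Skips were more probably coded or not counted as missing. Detectable effects worked out on that basis would also rest on an assumed prevalence, and would set the standard deviation among smokers against that among all students.

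The reply does not close the point. A response rate counts students, and an interview can be complete while containing legitimate skips. Skip instructions settle which questions are asked, not how an unasked question is scored. If skips were coded, the code is not given. If they were not counted as missing, the score formula is needed. For the five hygiene items there is no suitable existing band or non-user answer to fall back on.

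**Conclusion.** The point holds, and most firmly for the oral hygiene score: five of its eleven items have no valid answer for a non-brusher or a never-attender, and the only rule for an item without a value is complete-case analysis. Applied as written, that can exclude these students. For the smoking score the same loss is possible, but only if D.2.2 is skipped and not placed in its lowest band. If the blank is filled with 0, the student receives the heaviest smokers' score on that item.

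The exclusion would depend on the outcome. Its size cannot be computed, because the documents give neither the prevalence of these behaviours nor the number of skips; the group-level figures above are illustrations on assumed rates. Only secondary outcomes are affected, not CPITN or S-OHI.

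A separate error lies next to this one. D.1 and D.3 score 2 for yes and 0 for no, against the SAP's own rule that preventive answers score highest. That is why, even with D.2.2 = 5, the lightest smoker in the table loses a point on quitting.

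**What to change.** Add structural scores to Appendix A:

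- B.1 = No: B1.1 and B.1.3 to B.1.6 take 0. B.1.7 keeps the student's actual answer, because it asks about tools other than the toothbrush and has its own 0 code.
- B.1.8 = No: B.1.9 to B.1.11 take 0.
- D.1 = No: D.2.2 takes 5, the existing score of its lowest band.

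State the formula for each domain score. Limit complete-case analysis to items that applied to the student and were left blank. Report the number of students in each domain score by group and visit.

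Correct D.1 and D.3 as well; until then the codes above do not make quitting reliably raise the smoking score. With those two items swapped (No = 2, Yes = 0), a never-user scores 2 + 4 + 5 + 2 + 4 = 17. The three smokers in the table score 14, 12 and 7, so quitting gains 3, 5 and 10 points.

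The cost is a few recoding lines, a short addition to the SAP and a rerun of the behavioural scores; no new data are needed. One limitation remains: a 0 ties never-attenders with students last seen three to five years ago on B.1.10, and with pain visits on B.1.11. B.1.8 and B.1.9 still separate them.
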